## PROTOCOL TITLE: Intervention to Improve Driving Practices Among High-Risk Teen Drivers

Participants will be sent informational texts to remind them to complete various aspects of the study. For example, participants may receive a text message two days before the scheduled survey date to remind them about the upcoming survey or contact the research team. These text messages will not include PHI or PII. Prior to the second meeting, the researcher will also make sure to send installation instructions if the teen and parent are interested in installing the devices before the next call. Once the teen and parent have received the study devices, there will be another video conference. During this meeting, the researcher will check to make sure that the devices and apps have been correctly installed and downloaded for the teen and parent. If the devices have not been installed, the researcher will help walk the teen and parent through the process. Once the devices have been installed the researcher will remind the teen and parent of any forms they did not complete. If they still have not completed them by the following week an email will be sent to the teen and parent as a reminder. This call should take about 30 minutes to an hour.

### **6.3 Describe:**

#### **6.3.1 Procedures performed to lessen the probability or magnitude of risks.**

All data collected will only be accessible to members of our research team. Data collected will be securely transferred to a protected research server at NCH and will be password-protected.

A Data and Safety Monitoring Committee (DSMC), comprised of an expert in Clinical and Translational Research with expertise in traffic injury and safety, a clinical psychologist who specializes in coping and adjustment issues for adolescents and their families, an injury researcher who specializes in technological applications and teen driving safety, and a state official who leads injury prevention efforts in the state of Ohio, has been established for the proposed study. The DSMC will collaborate with our research team throughout the duration of the study.

The secure Azūga™ Amazon Web server and the secure NCH server will be utilized to protect all study data, and in particular data collected from the in-vehicle device (e.g., GPS data). Several precautions will be taken to protect participant confidentiality and privacy. These include:

1. Anonymizing participants (only using Azūga™ participant aliases, rather than their real names),
2. Isolating data (storing our data on a physically isolated drive separate from all other Azūga™ clients' data),
3. Controlling access (only our research team will be able to access the data),
4. Monitoring data remotely (designated research staff can monitor participants' data remotely at any time),
5. Keeping individually identifiable private information in a separate file that is only accessible to the PI and authorized researchers,
6. Representing participants by computer-assigned case numbers, instead of names, images, and/or specific identifiers,
7. Maintaining all data on password-protected computers and keeping hard copies of the data in a locked file cabinet only accessible by our research team.

Additionally, we will use advanced computer informatics to ensure data is secure (e.g., epsilon-differential privacy), which provides mathematically rigorous guarantees regarding the presence or absence of a particular user's entry in the database, and fully homomorphic encryption, which enables computation of encrypted data without disclosure to ensure the confidentiality of processed data. NCH also has an established committee, the Privacy and Security Advisory Committee (pSAC), which is dedicated to ensuring that study information, particularly information pertaining to study participants, is securely maintained and follows applicable laws and regulations.

#### **6.3.2 The source records that will be used to collect data about subjects. (Attach all surveys, scripts, and data collection forms.)**

See Attached

**6.4 What data will be collected during the study and how that data will be obtained.**

1. Risky driving events (hard braking, sudden acceleration, speeding): will be collected among teens in all three groups using the Azūga™ in-vehicle device. The number and type of driving event, including hard braking ( $\leq -0.45$  g-force) sudden acceleration ( $> 0.35$  g-force), and speeding ( $>10$  miles over the posted speed limit), and speed  $>75$  mph will be automatically coded and counted in the system. The rates will be computed by dividing events by miles driven then multiplying by 1,000.
2. Unsafe driving behaviors: Using the Azūga™ in-vehicle device and smartphone app, we will collect data on teen's unsafe driving behaviors (e.g., speeding, no seatbelt use). The duration (e.g., miles driven) and type of driving behaviors, including speeding ( $>10$  miles over the posted speed limit), will be automatically coded and counted in the system. The proportions will be calculated by dividing by miles driven then multiplying by 1,000 (e.g., proportion of 1,000 miles in which speeding). In addition, surveys will collect self-reported distracted driving (e.g., calls made and received, texts sent and viewed while driving, searches for a webpage/app) and seatbelt use (since not all vehicle models are available via Azūga™ in-vehicle device).
3. Parent-teen communication: Frequency of parent-teen communication: Dyads will be asked to rate the frequency of parent-teen conversations on each of the 24 common driving skills/safety principles, discussed in the past month (0=*never* to 3=*often*) and level of success (1=*poor* to 10=*excellent*). Frequency of parent-teen communication scores will range from 0 to 72, with higher scores indicating more frequent communication. Quality of parent-teen communication scores will be calculated by averaging ratings for all skills/principles addressed, and then weighting them based on the maximum score possible, and then recording scores as a percentage (possible range= 1% - 100%). Additionally, quality of parent-teen communication will be assessed using voice recorded dyad conversations (one conversation submitted per survey). Conversations will be coded by two trained coders with established inter-rater reliability who will identify if parents 1) use active listening; 2) use "OARS"; 3) solicit input about the teen's perspective, 4) focus on objective behaviors, and/or 5) express emotional responses, with each item scored individually (0=*never* to 3=*often*). A summary score for each conversation will be calculated.
4. Recidivism will be measured among teens in all three groups by linking traffic citations and court disposition data with the participating teen's driver's license number. Recidivism during the 12 months following study completion, including date and type of violation, and days from index violation to subsequent violation will be analyzed. The time of recidivism may not be observed when the 12-month study participation is completed and thus, it will be considered as censored at month 12 (end of study participation).
5. Engagement with device feedback will be measured among teens in Group 2 (Driving Feedback Only) & Group 3 (Driving Feedback plus Parent Training) and parents in Group 3 via online tracking of the participant's web interface using Google Analytics. The number of times each of the driving summaries is accessed (links clicked), and the amount of time spent at each link will be recorded.
6. Engagement with the parent communication training will be measured among parents in Group 3 (Driving Feedback plus Parent Communication Training) using a self-report questionnaire and via online tracking. Self-report: Following the individualized training, and at 3- and 6-months follow-ups, parents will report: (i) how frequently they have used communication strategies in their parent-teen discussions on safe driving during the past month (0=*never* to 3=*often*), (ii) how helpful these strategies and techniques have been (1=*not helpful at all* to 10=*extremely helpful*), and (iii) their perceived level of mastery of the strategies and techniques (1=*poor* to 10=*excellent*). Summary scores will be calculated. Online tracking: Using Google Analytics, parents' interactions with the online parent-teen safe driving communication guide will be tracked, including the number of logins, visited sub-links, and time spent at each link.

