### 2.2 State the hypotheses to be tested.

Aim 1: Hypotheses: The two intervention groups will demonstrate significant reductions in risky driving events (hard braking, sudden acceleration, speeding) and unsafe driving behaviors (speeding, no seatbelt use, distracted driving) per 1,000 miles driven when compared to the control group; The Driving-Feedback plus Parent Communication Training group will have fewer risky driving events and unsafe driving behaviors than the Driving Feedback Only group.

Aim 2: Hypothesis: The Driving-Feedback plus Parent Communication Training group will engage in more frequent and higher quality parent-teen communications on safe-driving topics than the other two groups.

Aim 3: Hypothesis: The two intervention groups will demonstrate significant reductions in recidivism (subsequent traffic violations) when compared to the Control group; The

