### **3.2 Describe any relevant preliminary data.**

We tested the feasibility of using in-vehicle driving feedback technology paired with parent communication training in a pilot in September 2017 at the Franklin County Juvenile Traffic Court. Teens and their parents were approached by a member of our research team following the teen's court hearing and invited to participate in the study. Interested parent-teen dyads were then screened for eligibility and then enrolled, if eligible. We enrolled 10 dyads (77% participation rate, 60% male, 90% first offense) within one week. Once the in-vehicle device and app were successfully installed/downloaded, we collected three weeks of driving data for each teen. Additionally, each parent was provided an individualized, virtual communication training (one week after enrollment) and a booster session (four weeks after enrollment) with a traffic safety communication specialist experienced in delivering the training. We instructed parents to review their teen's cumulative driving data and an online version of the parent-teen safe driving communication guide. Parents were also provided with a voice recorder to record and submit a 3-minute parent-teen conversation about safe driving following the initial parent communication training session. This recorded parent-teen conversation was used by the communication specialist to tailor the respective booster sessions and to assess intervention fidelity.

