## 5.0 Study Intervention/Investigational Agent

### 5.1 Description: Describe the study intervention and/or investigational agent (e.g., drug, device) that is being evaluated.

**In-vehicle Driving Feedback Technology:** The Azūga™ in-vehicle driving feedback technology, which consists of a pager-sized device plugged into the vehicle's on-board diagnostic port (installed in the teen's car) and a smartphone app (downloaded on the teen's smartphone), will be installed/downloaded. Four types of feedback will be provided to intervention teens: 1) Direct audio feedback from the installed device; 2) Push notification on the phone screen when a trip ends; 3) Detailed cumulative driving data; and 4) A customized biweekly driving summary report.

**Parent Training:** An individualized virtual training in communication strategies about driving safety along with a booster session will be delivered by a traffic safety communication specialist to parents in the Driving Feedback plus Parent Communication Training group. Parents in this group will also be provided with access to their teen's driving data as well as an online parent-teen safe driving communication guide.

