### **11.0 Vulnerable Populations\***

#### **11.1 If the research involves individuals who are vulnerable to coercion or undue influence, describe additional safeguards included to protect their rights and welfare.**

Participating in the study will not affect a participant's court hearing. Clinical services will not be provided as part of this study. To ensure individuals are not coerced to participate in the study by the court, all meetings between participants and research staff, including the initial meeting at the courthouse, will occur only after the teens' court hearing and after they have received the judge's final decision. No court officials will be involved in the recruitment process or implementation of the study protocols and intervention. Additionally, the judge will be blinded from the identity of any teens and parents who choose to participate in the study.

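### The recorded-conversation score, the only Aim 2 measure not self-rated by the dyad, rests on judgement ratings by coders whom the plan neither masks to group nor separates from intervention staff

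*Combined protocol and SAP*

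**What the plan says.** Section 6.4 item 3 gives two kinds of communication measure. The dyads themselves rate how often they discuss 24 topics and how successful those conversations are. In addition, one recorded conversation per survey is rated for quality: "Conversations will be coded by two trained coders with established inter-rater reliability". The coders are to "identify if parents 1) use active listening; 2) use 'OARS'; 3) solicit input about the teen's perspective", and also to judge focus on objective behaviours and expression of emotional responses. Each item is rated from 0 (never) to 3 (often), and a summary score is formed by a rule that is not given.

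Section 5.1 describes what Group 3 parents alone receive: "An individualized virtual training in communication strategies about driving safety along with a booster session". The Aim 2 hypothesis in section 2.2 is that this group "will engage in more frequent and higher quality parent-teen communications on safe-driving topics than the other two groups". Section 17.1 analyses each communication outcome by ANCOVA across the three groups.

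The blinding statements (sections 6.2, 11.1 and 13.1) concern juvenile court personnel only, and cover who takes part, not which group they are in. Sections 6.3.1, 17.2 and 24.4 replace names with case numbers, IDs or pseudonyms. Section 17.3, on quality control of collected data, is answered as not applicable.

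**The concern.** How often a parent listens actively, or invites the teen's view, is a matter of judgement. A coder who knows that a parent was trained, or that a recording was made after training, also knows which way the study expects the score to go. Inter-rater reliability does not address this, since two coders with the same expectation can agree closely and both be wrong in the same direction. ANCOVA does not address it either: a scoring shift that follows group is indistinguishable from a treatment effect, and adjusting for baseline does not correct biased follow-up ratings.

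The frequency and success ratings come from parents and teens who know what they received. The recording is therefore the one Aim 2 measure for which masked assessment is possible, and the plan as written does not secure it.

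**Working it through.** **Text check.** Four protections were looked for in the protocol.

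| Protection for the coded score | Found? |
|---|---|
| Coders masked to group | No |
| Coders masked to visit or date | No |
| Coders separate from training, booster or fidelity staff | No |
| Agreement between coders | Yes, 6.4 item 3 |

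The ID and pseudonym rules hide names. They do not say that group or visit is hidden from coders.

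**Illustration of size.** The plan gives no figure to reproduce: no SD, summary formula or effect size is stated for this score.

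Inputs:
- n = 74 per group (section 17.1, where it is the sample size used for Aim 1 power).
- Assumed: summary score is the plain sum of five items, range 0 to 15.
- Assumed: SD between 2.5 and 3.5.
- Assumed: no true effect, and two-sided alpha 0.05 for each comparison.
- Assumed: coders lean toward Group 3 by 0.1 or 0.2 point on every item, a total lean L of 5 × 0.1 = 0.5 or 5 × 0.2 = 1.0.

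Formulas (normal approximation):
- Standardised shift d = L / SD.
- Mean of the test statistic m = d × √(n/2) = d × √37 = d × 6.083.
- Against one comparator: P(|Z + m| > 1.96).
- Against both: P(Z₁ + m > 1.96 and Z₂ + m > 1.96), with correlation 0.5 between Z₁ and Z₂ because both contrasts share Group 3.

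| L | SD | d | m | One comparator | Both comparators |
|---|---|---|---|---|---|
| 0 | any | 0 | 0 | 5% | 0.5% |
| 0.5 | 3.5 | 0.143 | 0.869 | 14% | 5% |
| 0.5 | 2.5 | 0.200 | 1.217 | 23% | 11% |
| 1.0 | 3.5 | 0.286 | 1.738 | 41% | 25% |
| 1.0 | 2.5 | 0.400 | 2.433 | 68% | 53% (0.535) |

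The last column matters most for Aim 2, because the hypothesis is superiority over both other groups.

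**Sensitivity to multiplicity.** Section 17.1 mentions adjustment for multiple comparisons only for the Aim 1 power statement. If two-sided alpha were 0.05/3, the chance of a false result favouring Group 3 over one comparator would be 12.0% at d = 0.2 and 51.6% at d = 0.4, against 0.8% with no lean. The inflation shrinks but remains.

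**The case against.** The strongest reply is that the protocol is silent, and silence is not a procedure. It does not say that coders will know the group, and section 6.3.2 refers data collection forms to attachments that are not in the text reviewed. That stands, so the point is a risk the plan leaves open and not a documented fault in conduct. It still needs action, because the remedy changes how recordings are labelled, ordered and assigned.

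A reader might infer from section 3.2 that the trainer will score the trial recordings, since in the pilot "This recorded parent-teen conversation was used by the communication specialist to tailor the respective booster sessions and to assess intervention fidelity". The documents do not support this. Every pilot parent was trained, so there was no group to mask, and the use was tailoring and fidelity, not outcome scoring. For the trial, section 6.4 does not link the two coders to the specialist. What remains is only that no separation is stated.

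It is also fair to object that the training content is never itemised, so overlap with the coded items is probable but not documented. Likewise the summary score may not be a plain sum, and the scoring direction of the emotional-response item is not stated, so a uniform lean over five items is a further assumption.

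A reader might also infer contamination of the driving results, because section 17.1 enters communication measures as covariates in a further driving model. That model adjusts for group. A constant shift in Group 3 is absorbed by the group terms, leaving the communication coefficient unchanged; only the group coefficient of that secondary model moves. The main Aim 1 model does not use the score.

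**Conclusion.** The point holds, at modest weight. The plan allows unmasked judgement scoring of the only communication measure rated from outside the dyad. Under the stated assumptions, a total lean of 0.5 point on a 0 to 15 score raises the chance of a false win over both comparators from 0.5% to between 5% and 11%; a lean of 1.0 raises it to between 25% and 53%. The SD, the lean and the summing rule are all assumed, so these figures show sensitivity and do not estimate this trial's error rate. They also count the whole lean, whereas masking would remove only the avoidable part.

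A reader might conclude that rater expectation alone could confirm Aim 2. That goes too far. The hypothesis also covers frequency, and the dyads rate both frequency and a separate quality score, neither of which the coders can affect. The bias reaches one of three secondary communication measures. Device-recorded driving events and court-record recidivism are not coder-rated.

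**What to change.** In section 6.4 item 3, specify that recordings from all groups and all surveys are stripped of group, date and visit labels, given a random code, and scored in one randomly mixed order. Specify that the outcome coders take no part in training, booster sessions or fidelity review, and that any recording used for tailoring or fidelity is reviewed for that purpose by someone else. Asking coders to record a guess of the group is an optional way to report how well masking worked.

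The cost is protocol wording, file renaming and a random list. The same two coders can be used provided they have no such intervention role; sample size and analysis do not change. There are two downsides: masking will be partial, because what parents say may reveal the training, and coding must wait for mixed batches and cannot be done as recordings arrive. The change should be made before coding starts, since the remedy for scores already made unmasked would be re-coding by new coders.

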**7.0 Data and Specimen Banking\***

- 7.1 If data or specimens will be banked for future use, describe where the specimens will be stored, how long they will be stored, how the specimens will be accessed, and who will have access to the specimens.**

## PROTOCOL TITLE: Intervention to Improve Driving Practices Among High-Risk Teen Drivers

Data will be stored on a secure password protected computer for 10 years following the completion of the study. Data will only be accessible by research team members on secure password protected computers.

### **7.2 List the data to be stored or associated with each specimen.**

Identifiable data (Names and contact information) will be kept to allow the research team to contact these participants for future studies our research team conducts that they may be eligible for. All de-identified data associated with the study will be kept for future research purposes.

### **7.3 Describe the procedures to release data or specimens, including: the process to request a release, approvals required for release, who can obtain data or specimens, and the data to be provided with specimens.**

Identifiable data will only be released to the research team at NCH or other institution approved to receive PII or PHI as part of the study. A written request for de-identified data must be placed through the PI and/or the required NCH channels. To receive the de-identified data from this study, the requestor must have an IRB that includes the use of the data or the study must be considered non-human research (e.g., analyzing existing data). De-identified data can be obtained by anyone with an approved request.

## **8.0 Sharing of Results with Subjects\***

### **8.1 Describe whether results (study results or individual subject results, such as results of investigational diagnostic tests, genetic tests, or incidental findings) will be shared with subjects or others (e.g., the subject's primary care physicians) and if so, describe how the results will be shared.**

If interested, the final study results will be shared with participants once they are available. Participants will provide an email or mailing address where we can send these results.

## **9.0 Study Timelines\***

### **9.1 Describe:**

#### **9.1.1 The duration of an individual subject's participation in the study.**

Participants will be enrolled in the study for a six-month period with 3 months of active intervention.

#### **9.1.2 The duration anticipated to enroll all study subjects.**

We anticipate it will take 35 months (study months 7 to 42) to recruit and enroll all participants.

#### **9.1.3 The estimated date for the investigators to complete this study (complete primary analyses)**

We anticipate the study to take approximately five years to complete.

